2.7 Statistical Analysis and Sample Size Justification

The PI, [name], will be responsible for analyzing all study data. The blind will be held at the local site by the VAPAHCS research pharmacist. Once all data has been cleaned and locked, [name] will be unblinded to conduct the final analyses.

Variables/Time Points of Interest

Objective and subjective sleep variables (total sleep time, sleep efficiency, wake after sleep onset, sleep quality) will be collected continuously during the 2-week baseline and the three-week intervention. Subjective alertness assessment will also be collected continuously over the five-week protocol. All of these will be used in the study analyses.

Statistical Methods

The purpose of this study is to test the hypothesis that ingestion of 10 mg of suvorexant 30 minutes prior to daytime sleep initiation in individuals working overnight shifts will significantly improve both objective (total sleep time, sleep efficiency, wake after sleep onset) and subjective (sleep quality) measures of sleep. A secondary goal is to test the hypothesis that ingestion of 10 mg of suvorexant 30 minutes prior to daytime sleep initiation will (1) increase subjective measures of alertness during the night shift and (2) decrease total sleep time during nocturnal sleep episodes on off-days. To accommodate the nested nature of the data (days nested within persons), analyses will be conducted in a multilevel modeling framework (19). Specifically, the total sleep time (TST), as an example, will be modeled as: $TST_{it} = \gamma_{00} + \gamma_{01} * group_i + u_{0i} + e_{it}$, where the TST obtained above for person i on day t , TST_{it} , are modeled separately as a function of between-person and within-person differences. Specifically, γ_{00} , indicates the expected TST score for a prototypical participant on a prototypical day (the reference category); γ_{01} captures between-group differences in sleep (placebo group vs. drug group); and u_{0i} and e_{it} capture additional between-person and occasion-specific differences not otherwise explained. All models will be fit using SAS 9.4 (proc mixed) with restricted maximum likelihood estimation. Effect size will be evaluated with respect to proportional reduction in unexplained variance from an informative baseline model (*pseudo-R²*, see (19)).

Exploratory measures:

While the primary measures in this study will examine *prospective* changes in sleep, we will also collect data that will

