examine *retrospective* changes in sleep. These include examining changes in subjective measures of sleep quality that are captured in the BSWSQ, ISI, and FOSQ-10 questionnaires. Changes on these questionnaires will be examined with repeated measure ANOVA. Another exploratory measure to be analyzed in the same manner will be a change in depressive symptom severity as captured on the CES-D. A final exploratory measure will be to examine the change in the number of caffeinated beverages during work shifts. Given that there is tremendous variability in the caffeine content of caffeinated beverages, within subject changes will be examined with multilevel modeling.

Power/Sample Size:

For estimation of sample size, we have reduced our aim to the single, most important outcome measure - will sleep efficiency improve in the drug condition - and reduced the statistical testing to a *t*-test. In previously published work (20), a variance of 3.62% - 3.87% was observed following use of 10 mg of suvorexant or placebo. For purposes of this sample size estimation, we can estimate $\sigma = 5.55\%$ (average variance * 150%, with the increase due to our use of actigraphy instead of polysomnography as a reporter). Setting $\alpha = 0.05$ and power = 80%, we would be able to detect a difference of 5.2% in sleep efficiency (i.e., that which was observed in a previous trial of 10 mg suvorexant in those with insomnia (21)) with 19 participants in each group (n=38 total).

**PROTOCOL
 APPLICATION FORM
 Human Subjects Research
 Stanford University**

Title : A double-blind, placebo-controlled, randomized, parallel design study to examine the effectiveness of 10 mg suvorexant in improving daytime sleep in shift workers

Approval Period: Draft

Protocol Director				
Name [name]		Degree (Program/year if student) PhD		Position, e.g. Assistant Professor, Resident, etc. Asst Professor
Department Psych/Sleep Medicine	Mail Code 5550	Phone [REDACTED]	Fax	E-mail [contact]
CITI Training current				Y

Admin Contact				
Name [name]		Degree (Program/year if student) BS		Position, e.g. Assistant Professor, Resident, etc.
Department Psychiatry and Behavioral Sciences	Mail Code 5550	Phone [REDACTED]	Fax	E-mail [contact]
CITI Training current				Y

Investigator				
Name		Degree (Program/year if student)		Position, e.g. Assistant Professor, Resident, etc.
Department	Mail Code	Phone	Fax	E-mail
CITI Training current				

Other Contact				

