g) Lead Investigator or Coordinating Institution in Multi-site Study.

Please explain (i) your role in coordinating the studies, (ii) procedures for routine communication with other sites, (iii) documentation of routine communications with other sites, (iv) planned management of communication of adverse outcomes, unexpected problems involving risk to participants or others, protocol modifications or interim findings.

1. Purpose

a) In layperson's language state the purpose of the study in 3-5 sentences.

The purpose of this study is to determine if suvorexant, a drug that inhibits a wake-promoting (hypocretin/orexin) system in the brain, is able to improve day time sleep and night time alertness in individuals who work night shifts.

b) State what the Investigator(s) hope to learn from the study. Include an assessment of the importance of this new knowledge.

There are currently no acceptable therapies to treat day time sleep difficulties in individuals who work night shifts (Shift Work Sleep Disorder). Current pharmacotherapies involve use of benzodiazepines or other sleep medications that put a person into an unnatural state of sleep. The medication being tested in this study blocks a very specific wake-promoting system in the brain that will enable individuals to achieve normal sleep during the daytime.

c) Explain why human subjects must be used for this project. (i.e. purpose of study is to test efficacy of investigational device in individuals with specific condition; purpose of study is to examine specific behavioral traits in humans in classroom or other environment)

The physiology of the drug-targeted system (hypocretin/orexin) being examined in this study is distinct in primates as compared with rodents and other non-mammalian species. The medical condition being examined (Shift Work Sleep Disorder) is uniquely human.

2. Study Procedures

a) Please SUMMARIZE the research procedures, screening through closeout, which the human subject

Title : A double-blind, placebo-controlled, randomized, parallel design study to examine the effectiveness of 10 mg suvorexant in improving daytime sleep in shift workers

Approval Period: Draft

will undergo. Refer to sections in the protocol attached in section 16, BUT do not copy the clinical protocol. Be clear on what is to be done for research and what is part of standard of care.

All procedures are done for research-purposes only.

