Baseline visit (3 hours): Consent process followed by baseline assessments using questionnaires, blood draw, urinalysis, electrocardiogram, and physical exam

Week 1-2: Sleep will be monitored with a wrist-worn device that monitors movement as well as participant-completed logs. No changes in behavior.

Weeks 3-5: Sleep will be continued to monitored as during baseline. Subjects will also take a pill 30 minutes prior to day time sleep attempts. This pill will have either drug or placebo (randomized)

End of study visit (2 hour): Same procedures as baseline visit.

- b) Explain how the above research procedures are the least risky that can be performed consistent with sound research design.**

All procedures in this study were designed with the goal of minimizing exposure to risk balanced with gaining a greater understanding of whether this treatment would help the individuals who participate in this study and for whom there is no currently available FDA-approved therapy.

- c) State if deception will be used. If so, provide the rationale and describe debriefing procedures. Since you will not be fully informing the participant in your consent process and form, complete an alteration of consent (in section 13). Submit a debriefing script (in section 16).**

Deception will not be used.

- d) State if audio or video recording will occur. Describe what will become of the recording after use, e.g., shown at scientific meetings, erased. Describe the final disposition of the recordings.**

Audio and video recordings will not occur.

- e) Describe alternative procedures or courses of treatment, if any, that might be advantageous to the participant. Describe potential risks and benefits associated with these. Any standard treatment that is being withheld must be disclosed in the consent process and form. (i.e. standard-of-care drug, different interventional procedure, no procedure or treatment, palliative care, other research studies).**

Instead of participating, individuals who work night shifts can use any one of a number of behaviors or medications to help them sleep during the day time. None of the available pharmacotherapies induce natural sleep and the behavioral therapies have efficacy in only a subset of individuals.

- f) Will it be possible to continue the more (most) appropriate therapy for the participant(s) after the conclusion of the study?**

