(i) We anticipate that we will enroll 38 participants to completion. We estimate that this will require 50 participants beginning the study (i.e., at least signing a consent form).
 (ii) This is a single-site investigation
 (iii) This study will examine healthy individuals who work at night and have difficulty initiating or maintaining sleep during the day. We are specifically studying the effectiveness of this medication on this condition.

- b) **State the age range, gender, and ethnic background of the participant population being recruited.**

Age: 20-60 years
 Gender: all
 Ethnicity: all with recruitment targeting the ethnicity distribution of individuals involved in night work in the catchment area

- c) **State the number and rationale for involvement of potentially vulnerable subjects in the study (including children, pregnant women, economically and educationally disadvantaged, decisionally impaired, homeless people, employees and students). Specify the measures being taken to minimize the risks and the chance of harm to the potentially vulnerable subjects and the additional safeguards that have been included in the protocol to protect their rights and welfare.**

Vulnerable subjects will not be specifically recruited.

- d) **If women, minorities, or children are not included, a clear compelling rationale must be provided (e.g., disease does not occur in children, drug or device would interfere with normal growth and development, etc.).**

Children are not included as they do not typically work night shifts and the effect of this drug on their developing brain is unknown.

- e) **State the number, if any, of participants who are laboratory personnel, employees, and/or students. They should render the same written informed consent. If payment is allowed, they should also receive it. Please see Stanford University policy.**

We are not specifically targeting laboratory personnel, employees, or students, though they are not explicitly excluded. Should they be recruited, they will sign the same consent as all subjects and receive payment as allowed.

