- f) **State the number, if any, of participants who are healthy volunteers. Provide rationale for the inclusion of healthy volunteers in this study. Specify any risks to which participants may possibly be exposed. Specify the measures being taken to minimize the risks and the chance of harm to the volunteers and the additional safeguards that have been included in the protocol to protect their rights and welfare.**

All participants will be healthy volunteers. The main risk to which they are exposed, over the risks they normally encounter in their lives, is taking a prescription medication. There is a favorable side-effect profile with minimal risk reported in taking this medication. The medication being prescribed is being used to specifically treat a sleep disorder in these volunteers.

- g) **How will you identify and recruit potential participants about the research study? (E.g., by: chart**

Title : A double-blind, placebo-controlled, randomized, parallel design study to examine the effectiveness of 10 mg suvorexant in improving daytime sleep in shift workers

Approval Period: Draft

review; notified by treating physician; response to ad). All final or revised recruitment materials, flyers, etc. must be submitted to the IRB for review and approval before use. You may not contact potential participants prior to IRB approval. See Advertisements: Appropriate Language for Recruitment Material.

Participants will be recruited by flyers and online advertising.

h) Inclusion and Exclusion Criteria.

Identify inclusion criteria.

- Aged 20-60 (older individuals excluded due to altered sleep-related circadian signaling)
- Males and females
- Shift worker
 - # Minimum of three months of prior shift work
 - # Will work minimum of four nights per week or 32 hours of night shift per week during study
 - # "Night work" defined as having at least six hours of work occurring between 8 PM and 8 AM and no longer than 12 hours on shift
- Presence of DSM-5 defined Circadian Rhythm Sleep-Wake Disorder: Shift Work Type
 - # Insomnia (SE < 88%) during attempted daytime sleep or excessive sleepiness during nocturnal wake

Identify exclusion criteria.

- Currently or planning to become pregnant
- Currently breastfeeding
- Inadequate opportunity (<7 hours) for daytime sleep after shift work
- Use of sleep aids during the study period. Includes as needed or continuous use of prescription, non-prescription, and naturopathic pharmacotherapies

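### The printed analysis model has no baseline sleep term, although two pre-treatment weeks are recorded and entry admits workers on either side of 88% daytime sleep efficiency

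*Combined protocol and SAP*

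**What the plan says.** **Who enters.** The inclusion criteria in section 8 h) require shift-work disorder shown by "Insomnia (SE < 88%) during attempted daytime sleep or excessive sleepiness during nocturnal wake". No exclusion criterion sets an SE limit, so a worker with night-time sleepiness and daytime SE of 88% or more is eligible. Section 8 a)(iii) is narrower. It describes night workers who "have difficulty initiating or maintaining sleep during the day. We are specifically studying the effectiveness of this medication on this condition".

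**What is collected.** Section 2.7 says that the objective and subjective sleep variables "will be collected continuously during the 2-week baseline and the three-week intervention", and adds: "All of these will be used in the study analyses". Under section 2 a), the pill is taken only in weeks 3-5: "This pill will have either drug or placebo (randomized").

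**What is modelled.** Section 2.7 prints one model, with TST as the example: an intercept, a group term, a person-level random intercept and a residual. The group coefficient "captures between-group differences in sleep (placebo group vs. drug group"). There is no baseline term and no term separating treated from untreated weeks. The baseline model mentioned in the same paragraph is a comparator for the pseudo-R² effect size, not a covariate.

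**What is powered.** The sample size uses SE and a t-test: 19 per group, sigma 5.55%, alpha 0.05, power 80%. The 5.2-point difference is the one "observed in a previous trial of 10 mg suvorexant in those with insomnia". Section 2 g), however, names change in daytime TST as the primary endpoint.

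**The concern.** With group as the only fixed effect, stable differences between people in how well they sleep by day stay in the error against which the treatment effect is judged. A two-week pre-treatment record would remove part of that error, and it is already being collected. The entry rule makes such differences likely, because it does not confine baseline SE to one side of 88%. An endpoint defined as a change also implies that baseline enters the analysis somehow, and the printed model does not say how.

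The general promise to use all the data leaves a second gap. It does not say whether week 1-2 days are outcome rows or baseline information. If they are outcome rows, the single group term averages untreated and treated days together.

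At stake are the precision of a 38-person trial whose planned power has almost no margin, and the freedom to choose a baseline adjustment after unblinding.

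**Working it through.** **Inputs from section 2.7, Power/Sample Size:** n = 19 per arm, difference 5.2, SD 5.55, alpha 0.05. Sidedness is not stated; two-sided reproduces the plan. (1.5 times the average of 3.62 and 3.87 is 5.62 rather than 5.55; the plan's 5.55 is used throughout.)

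**Assumptions not in the documents:** the correlation ρ between a participant's week 1-2 mean and weeks 3-5 mean; 5.55 is an unadjusted on-treatment SD; the drug effect does not vary with baseline. The analysis is of person means, as in the plan's own sizing.

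**Step 1: reproduce the plan.** Standard error = 5.55 × √(2/19) = 1.801. Noncentrality = 5.2 / 1.801 = 2.888 on 36 df. The noncentral t gives power of 80.2%, and 19 is the smallest n per arm that reaches 80%. The difference detectable with 80% power is 5.18, so there is almost no slack.

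**Step 2: add a continuous baseline covariate.** The residual SD becomes 5.55 × √(1 − ρ²) and one degree of freedom is lost (35 df). Chance imbalance in the covariate inflates the variance by about 1 + 1/(2n − 4) = 1 + 1/34. So the standard error is 5.55 × √(1 − ρ²) × √((2/19)(1 + 1/34)).

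| ρ (assumed) | Residual SD | Standard error | Noncentrality | Power |
|---|---|---|---|---|
| 0 | 5.55 | 1.827 | 2.85 | 79% |
| 0.3 | 5.29 | 1.743 | 2.98 | 83% |
| 0.5 | 4.81 | 1.582 | 3.29 | 89% |
| 0.7 | 3.96 | 1.305 | 3.99 | 97% |

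Simulation with simple randomisation gives the same rounded figures. Without the covariate, power stays at 80% in every row.

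**Step 3: which rows are outcomes.** If all five weeks were outcome rows with equal days per week, the group term would estimate 5.2 × 3/5 = 3.12 points, because two of the five weeks are untreated. A baseline covariate does not correct this. The outcome rows must be limited to weeks 3-5.

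**Step 4: what the 'or' does to the 80%.** Let f be the share entering on sleepiness alone and e their SE gain. The mean difference is (1 − f) × 5.2 + f × e. The documents give neither f nor e. Holding SD at 5.55 with no covariate:

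| f | e = 5.2 | e = 2.6 | e = 0 |
|---|---|---|---|
| 20% | 80.2% | 71.5% | 61.3% |
| 30% | 80.2% | 66.6% | 50.3% |
| 50% | 80.2% | 55.9% | 29.0% |

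The range runs from no loss to a large loss, and nothing in the plan locates the trial within it.

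**The case against.** **The model is only an example, and baseline data are promised a use.** This is fair: applying the printed model to SE is an inference, and a change endpoint suggests that some use of baseline was intended. But no other model is printed for the sleep outcomes, and neither statement says how baseline enters. The gap is one of specification, and that part of the point stands.

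**Baseline adjustment is general advice that owes nothing to the entry rule.** Correct. The gain in Step 2 arises with equal response in everyone. The 'or' is a reason to expect baseline SE on both sides of 88%, not the source of the gain.

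**5.55 may not be an unadjusted SD.** This also stands as a caveat. Section 2.7 says only that the variation was observed after drug or placebo. If the source figure was already a change or adjusted SD, Step 2 counts the gain twice.

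**A reader might infer that the 'or' makes the trial underpowered.** The documents do not support that. Without the share and response of sleepiness-only entrants, no loss is shown, and with equal response there is none. Nor does the calculation need 5.2 points within each route. A t-test needs a mean of 5.2 over those enrolled, and the plan openly names its source population. What is missing is a statement carrying that figure over to the enrolled mix.

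**A reader might also conclude that entry should be restricted.** The purpose in section 1 a), whether the drug "is able to improve day time sleep and night time alertness in individuals who work night shifts", is compatible with both routes. Which population is meant is for the investigators to settle.

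**Conclusion.** The point holds as a gap in the analysis specification. The only printed model ignores a pre-treatment record that the trial already collects, and it does not say which weeks supply the outcome. Under the stated assumptions, a continuous baseline covariate moves power from 80% to between 79% (ρ = 0) and 97% (ρ = 0.7), with 89% at ρ = 0.5. These figures concern SE only; TST, named primary in section 2 g), has no sizing of its own. The trial is not invalid without the change, but the downside is about one power point and the possible gain is considerable, so it should be made before unblinding.

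Two lesser points also hold. Sections 8 a)(iii) and 8 h) describe different populations. The 80% figure rests on an unstated assumption that the mean SE difference over the enrolled mix is 5.2 points. The covariate improves precision but would not restore a mean effect that was diluted, so that assumption has to be stated separately.

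**What to change.** 1. **Section 2.7, Statistical Methods.** Add: *The models for daytime sleep outcomes will be fitted to daytime sleep episodes in weeks 3-5 only. Each participant's week 1-2 mean of the same outcome will be a continuous fixed effect (actigraphy daytime SE in the SE model, daytime TST in the TST model). All randomised participants will be included.* The text should also say how a missing baseline mean is handled, since otherwise the software drops that participant.
2. **Section 2.7, Power/Sample Size.** Add: *The 80% power assumes a mean SE difference of 5.2 points over the enrolled mix of entry routes (insomnia and night-time sleepiness alone).*
3. **Sections 8 a)(iii) and 8 h).** Reconcile the description of participants with the entry criterion.

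The cost is one covariate and a few sentences, with no new measurement, visit or participant. One degree of freedom is spent, which together with chance covariate imbalance takes 80.2% to about 79% if baseline proves uninformative. Stratified assignment by baseline SE is not needed. In simulation with correlations up to 0.7 it added at most about 0.6 power points to the covariate, and it would require actigraphy to be scored before assignment.

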After conclusion of the study, participants would be able to contact their physicians to obtain a prescription for the medication used in this study.

- g) Study Endpoint. What are the guidelines or end points by which you can evaluate the different treatments (i.e. study drug, device, procedure) during the study? If one proves to be clearly more effective than another (or others) during the course of a study, will the study be terminated before the projected total participant population has been enrolled? When will the study end if no important differences are detected?**

The primary endpoint of this study is a change in total sleep time during day time sleep episodes. Given the blinding of the study and the relatively small population being studied, we do not intend to examine the primary outcome prior to study completion (38 total subjects).

3. Background

- a) Describe past experimental and/or clinical findings leading to the formulation of the study.**

The hypocretins (orexins) are a pair of neuropeptides produced by a small group of hypothalamic neurons

Title : A double-blind, placebo-controlled, randomized, parallel design study to examine the effectiveness of 10 mg suvorexant in improving daytime sleep in shift workers
Approval Period: Draft

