- Diagnosis or detection (during study) of sleep disordered breathing (AHI>10) on home sleep testing; referral to clinical sleep program will be offered
- Diagnosis of narcolepsy
- Restless Legs Syndrome
- >600 mg caffeine intake per night shift or use of prescription stimulant medication during night shift
- Rotational or irregular work shifts during study
- Use of digoxin for six months prior to or during study
- Use of strong (e.g., etoconazole, itraconazole, posaconazole, clarithromycin, nefazodone, ritonavir, saquinavir, nelfinavir, indinavir, boceprevir, telaprevir, telithromycin, conivaptan) or moderate (e.g., amprenavir, aprepitant, atazanavir, ciprofloxacin, diltiazem, erythromycin, fluconazole, fosamprenavir, grapefruit juice, imatinib, verapamil) CYP3A inhibitors or CYP3A inducers (e.g., rifampin, carbamazepine, phenytoin) for six months prior to or during study
- Severe hepatic impairment
- Unstable or severe medical or psychiatric condition

i) Describe your screening procedures, including how qualifying laboratory values will be obtained. If you are collecting personal health information prior to enrollment (e.g., telephone screening), please request a waiver of authorization for recruitment (in section 15).

Screening procedures will be done in a private room at VAPAHCS. Laboratory values will be obtained after a nurse draws blood and collects urine from the participant at the VAPAHCS Clinical Studies Unit.

j) Describe how you will be cognizant of other protocols in which participants might be enrolled. Please explain if participants will be enrolled in more than one study.

We will ask subjects during the recruitment and screening process whether they are enrolled in any other study. Participants enrolled in other studies will not be enpaneled in this study.

k) Payment/reimbursement. Explain the amount and schedule of payment or reimbursement, if any, that will be paid for participation in the study. Substantiate that proposed payments are reasonable and commensurate with the expected contributions of participants and that they do not constitute undue pressure on participants to volunteer for the research study. Include provisions for prorating payment. See payment considerations

Title : A double-blind, placebo-controlled, randomized, parallel design study to examine the effectiveness of 10 mg suvorexant in improving daytime sleep in shift workers

Approval Period: Draft

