Subjects will be paid [REDACTED] for completing all aspects of the protocol, not including screening. This will be broken down as: [REDACTED] per week of study (5 weeks = [REDACTED] + [REDACTED] completion incentive. This is payable after completion of the individual's study. Individuals who complete only part of the study will receive a prorated amount, not including the completion incentive.

l) Costs. Please explain any costs that will be charged to the participant.

Participants will not be charged for engaging in this study.

m) Estimate the probable duration of the entire study. Also estimate the total time per participant for: (i) screening of participant; (ii) active participation in study; (iii) analysis of participant data.

We estimate that that study will take two years to complete subject empanelment and analysis. Screening participants will take approximately three hours each. Participants will then be active in the protocol for five weeks. Analysis of data will take approximately 6 months.

9. Risks

- a) For the following categories include a scientific estimate of the frequency, severity, and reversibility of potential risks. Wherever possible, include statistical incidence of complications and the mortality rate of proposed procedures. Where there has been insufficient time to accumulate significant data on risk, a statement to this effect should be included. (In describing these risks in the consent form to the participant it is helpful to use comparisons which are meaningful to persons unfamiliar with medical terminology.)

The risks of the Investigational devices.

None

The risks of the Investigational drugs. Information about risks can often be found in the Investigator's brochure.

None

The risks of the Commercially available drugs, reagents or chemicals. Information about risks can often be found in the package insert.

There is a risk of an unknown side-effect from taking this FDA-approved medication. The most common side-effect is sleepiness. As such, we require that subjects only take the medication when they have at least 7 hours of time to sleep.

The risks of the Procedures to be performed. Include all investigational, non-investigational and non-invasive procedures (e.g., surgery, blood draws, treadmill tests).

There is the possibility of a small scar to form at the site of venipuncture. This risk is increased in individuals with darker skin pigmentation.

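### Does the sleep-aid exclusion, which runs through the randomised weeks, let treatment decide who is analysed?

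*Combined protocol and SAP*

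**What the plan says.** Among the exclusions in section 8h is "Use of sleep aids during the study period. Includes as needed or continuous use of prescription, non-prescription, and naturopathic pharmacotherapies". It has no look-back period, whereas the digoxin item beside it does: "Use of digoxin for six months prior to or during study". Section 2a sets a two-week baseline without study drug, then the treatment phase: "Weeks 3-5: Sleep will be continued to monitored as during baseline". In those weeks a pill is taken before daytime sleep, and "This pill will have either drug or placebo (randomized").

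On numbers, section 8a states "We anticipate that we will enroll 38 participants to completion" and expects 50 people to sign consent to reach that figure. The power paragraph of section 2.7 arrives at the same total, "with 19 participants in each group (n=38 total"). Section 2g says of interim looks that "we do not intend to examine the primary outcome prior to study completion (38 total subjects").

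Section 2.7 specifies a multilevel model for days within persons, fitted by restricted maximum likelihood. It names no analysis population and gives no rule for deviations or withdrawals. Partial completion appears only under payment, in section 8k: "Individuals who complete only part of the study will receive a prorated amount, not including the completion incentive". Section 2.7 also has the research pharmacist hold the blind and unblinds the analyst only after the data are cleaned and locked.

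**The concern.** Apart from an intention declared at screening, this criterion can be met only by what a participant does once in the study, and three of the five weeks fall after randomisation. Taking a sleep aid is a plausible response to poor daytime sleep, which is what the trial measures. If suvorexant works, such use may be commoner on placebo.

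If users were then removed and others enrolled until 38 had finished, the worst placebo sleepers would be under-represented. The comparison would no longer be by randomised group, and a real effect would be understated. With no analysis set written down, the analysed group could also be settled after unblinding. At stake are a fraction of the planned 5.2-point difference in sleep efficiency and some of the 80% power.

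**Working it through.** **Inputs from section 2.7.** Difference 5.2 points of sleep efficiency, SD 5.55, alpha 0.05, power 80%, 19 per group. Section 2g names total sleep time as the primary endpoint, but only sleep efficiency is given an SD, so the check uses it.

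**Inputs not in the documents (assumed).** Share of participants using sleep aids: 10% placebo vs 5% drug, up to 20% vs 5%. Correlation r between use and poor sleep: 0.3 to 0.5.

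**1. The plan's own figure.** A two-sided two-sample t-test (noncentral t) with 19 per group has power 80.2%, so the stated size reproduces. It contains no allowance for loss.

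**2. What the text orders.** Set side by side:
- Section 8h lists conditions of eligibility. Other items in the list also look ahead, such as the minimum night work to be done during the study and the bar on irregular shifts. These are checked at entry as commitments.
- Section 8a is an enrolment forecast. Its gap of (50 - 38)/50 = 24% is counted from consent, so it includes screen failures and is not a rate of loss after randomisation.
- No section says that a randomised participant who takes a sleep aid leaves the study, loses their data or is replaced.
- The criterion also covers the two baseline weeks, before any pill. Removal for use found then cannot depend on treatment.

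**3. If users were removed.** When a fraction f of an arm is removed, the mean of those kept rises by r × 5.55 × φ(z_f)/(1 - f). For r = 1 this is:
- f = 5%: 5.55 × 0.1031/0.95 = 0.60
- f = 10%: 5.55 × 0.1755/0.90 = 1.08
- f = 20%: 5.55 × 0.2800/0.80 = 1.94

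Bias is the placebo rise minus the drug rise. Power below is at SD 5.55; without replacement, 17/18 or 15/18 are analysed (placebo/drug).

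| Removed (placebo vs drug) | r | Bias | Difference left | Power, replaced | Power, not replaced |
|---|---|---|---|---|---|
| 10% vs 5% | 0.3 | 0.14 | 5.06 | 78.0% | 74.4% |
| 10% vs 5% | 0.5 | 0.24 | 4.96 | 76.4% | 72.7% |
| 20% vs 5% | 0.3 | 0.40 | 4.80 | 73.7% | 66.8% |
| 20% vs 5% | 0.5 | 0.67 | 4.53 | 68.7% | 61.9% |

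Part of the last column is only the smaller sample: unbiased loss to 17/18 or 15/18 gives 76.7% or 73.8%. Equal removal in both arms gives zero bias. The extreme case, perfectly selective removal of 10% to 20% from placebo alone, gives bias 1.08 to 1.94.

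**4. If users were kept.** Sleep-aid days can raise placebo sleep. The contrast shrinks by (placebo share - drug share) × share of days × gain on those days:
- Lightest case: 0.05 × 0.25 × 2.6 = 0.03, power 79.7%
- Half of days: 0.15 × 0.50 × 5.2 = 0.39, power 73.9%
- Every day, 10% vs 5%: 0.05 × 5.2 = 0.26, power 76.1%
- Every day, 20% vs 5%: 0.15 × 5.2 = 0.78, power 66.6%

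**5. Comparison.** At the same rates of use, removal costs 0.14 to 0.67 points. Retention costs 0.03 to 0.39 if aids are used on 25% to 50% of days, and 0.26 to 0.78 if used daily at full benefit. The ranges overlap, and which is larger depends on assumptions the documents cannot settle.

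**The case for a change.** The case for a change is that the words of section 8h do reach past randomisation, that 38 is both the number of completers and the powered number, and that nothing shown prevents removal and replacement. If an entry condition is meant, one sentence would say so, at no cost in participants and with the planned model unchanged. Locking the data fixes the values, not the set of people analysed, and the analyst is then unblinded.

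Most of this stands as description. A stated analysis set would be better practice, and it would cover the other items worded over the study period as well (irregular shifts, CYP3A inhibitors, sleep-disordered breathing found during the study). What does not stand is the step from silence to a biased comparison. That step needs a removal rule and a replacement rule, and the plan contains neither. Withdrawals during conduct would be decided with the blind in force.

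The argument that a rule fixed in advance protects the randomised comparison is sound in principle. How sleep-aid days should count is nevertheless a choice of estimand: the effect with such use included, or the effect in its absence. Reasonable statisticians differ on that choice here.

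A false positive is also possible in theory. With no drug effect but removal of 20% vs 5% at r = 0.5, simulation rejects 6.8% of the time instead of 5%. That needs unequal removal without a treatment effect to cause it.

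**Conclusion.** No change is called for. The concern identifies missing detail, an unwritten analysis set and deviation rule, and not a stated rule that gives a wrong result. The ordinary way to fill the gap is to analyse all randomised participants who have daytime sleep records in weeks 3-5, in the group assigned, and to report sleep-aid use by arm as a deviation. The planned mixed model already accepts unequal numbers of days per person.

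If users were nonetheless removed, the loss would be 0.14 to 0.67 of 5.2 points, with power 69% to 78% when replaced. This rests wholly on assumed rates and correlations and on a t-test for sleep efficiency in place of the planned model. Keeping them could cost a similar amount, up to 0.78 points and power 67% with daily use. The true size and direction cannot be derived from the documents. The sections of the statistical document before 2.7 are not in the text available, so rules on conduct may be stated there.
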